8.4 Methods for statistical analyses

In this open-label, Phase Ib study, no formal hypothesis testing will be conducted. Descriptive statistical and graphical displays will be employed to assess the safety, PK data, and preliminary anti-tumour activity by dose level cohort.

A comprehensive description of the statistical analyses and data summaries for this study will be documented in a Statistical Analysis Plan (SAP).

The study will have a primary data cut-off for the primary analysis (see Section 9.3). Following the primary analysis data cut-off, no further statistical analysis of the data will be conducted. All safety data collected after the primary analysis and up to (and including) the last of the FPVs will be listed and/or summarised as appropriate. A CSR addendum will be prepared to include such data.

8.4.1 Demographic and baseline data

Baseline characteristics of the patients, including demography, medical history, disease characteristics, and prior therapies will be listed for each patient and summarised by dose level cohort.

8.4.2 Exposure

Exposure to AZD1775 (i.e., total amount of study drug received) will be listed and summarised by dose level cohort. Total exposure, time on study drug, and dose intensity will be summarised, along with the number and percentage of patients with at least one dose interruption and at least one dose reduction. Reason for discontinuation of study treatment will be summarised.

8.4.3 Safety

Dose-limiting toxicities will be summarised by dose level cohort using the DLT analysis set. Additionally the following minimum data summaries will be presented by dose level cohort using the full analysis set:

- TEAEs of any CTCAE grade – summarised by MedDRA preferred term and system organ class and CTCAE maximum grade

- SAEs
- Deaths summarised by primary cause
- Laboratory parameters (hematology and chemistry), vital signs, ECG data and concomitant medications including evaluations for potential DILI

8.4.4 Efficacy

Anti-tumour activity will be summarized using the full analysis set.

8.4.5 Best objective response

The best objective response to treatment via RECIST v1.1 and Investigator assessment will be summarised by dose level cohort.

The best objective response (BOR) per subject will be derived as the best response recorded from the start of treatment until disease progression, death or subsequent cancer therapy (taking as reference for progressive disease the smallest measurements recorded since treatment started) using the Investigator reported objective response per time point. See [Appendix E](#) for how objective visit responses will be recorded.

Objective Response Rate (ORR) is the proportion of patients whose confirmed best objective response is complete response (CR) or partial response (PR). Confirmation must occur at least 4 weeks later.

Only patients with measurable disease will be included in the analysis of ORR. Patients without measureable disease at baseline will be excluded in the analysis of ORR.

The following rules will be used to determine the best objective response in each patient, assuming Assessment 1 is Baseline/Pre-treatment tumour assessment, and assessments are performed every 8 weeks on the BID and QD 5/9 Schedule or 9 weeks on either of the 5/2 Schedules.

Assessment 2	Assessment 3	Assessment 4	Best Objective Response
PD	-	-	PD
CR, PR, SD	PD	-	SD
UNK	PD	-	PD
CR, PR or SD	UNK	PD or UNK	SD
SD or UNK	CR, PR or SD	PD	SD
UNK	UNK	PD	PD

Assessment 2	Assessment 3	Assessment 4	Best Objective Response
PR	SD ⁽¹⁾	PD	SD
PR	CR or PR	PD or UNK	PR
PR	SD	PR	PR
PR	UNK	PR	PR
CR	CR	PD	CR
CR	UNK	CR	CR

(1) Only if the increase in diameter from Assessment 2 to Assessment 3 does not qualify for PD

- **Objective Response Rate (ORR)** = Proportion of patients with a confirmed best objective response of CR or PR.

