2.2 Secondary objectives

Secondary Objective :	Outcome Measure :
To evaluate the safety and tolerability of AZD1775 monotherapy in patients with locally advanced or metastatic solid tumours.	Treatment-emergent adverse events (TEAEs) and SAEs
To evaluate the preliminary anti-tumour activity of AZD1775 monotherapy in patients with locally advanced or metastatic solid tumours.	Best objective response (OR) to treatment will be assessed by dose level cohort according to Response Evaluation Criteria in Solid Tumours (RECIST) v1.1 (Eisenhauer et al 2009).
To evaluate the PK profile of AZD1775 monotherapy in patients with locally advanced or metastatic solid tumours.	PK parameters of AZD1775
To evaluate the preliminary effect of a high-fat meal on the PK profile of AZD1775 monotherapy in patients with locally advanced or metastatic solid tumours.	PK parameters of AZD1775
To characterise the effect of AZD1775 on QTc interval in patients with locally advanced or metastatic solid tumours.	QTc interval

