8.3 Outcome measures for analyses

8.3.1 Tumour response

Patients will undergo regular tumour assessments until documented objective disease progression as defined by RECIST v1.1. At each restaging visit the RECIST data for a patient will be assigned a response of CR, PR, SD, or PD depending on the status of the disease compared with baseline and previous assessments (see [Appendix E](#)).

The objective response rate (ORR) is defined as the number of patients with a confirmed best objective response (OR) of CR or PR divided by the number of patients in the full analysis set. Similarly, the disease control rate (DCR) is defined as the percentage of patients in the full analysis set with a confirmed best objective response of CR or PR, or a best objective response of SD.

Progression of TL will be calculated in comparison with what the tumour burden was at a minimum (i.e., smallest sum of diameters previously recorded on study). In the absence of

progression, tumour response (CR, PR, or SD) will be calculated in comparison to the baseline tumour measurements obtained before starting treatment.

If a patient has had a tumour assessment that cannot be evaluated, then the patient will be assigned a visit response of NE (unless there is evidence of progression in which case the response will be assigned as PD).

For TL measurements, if $\leq 1/3$ of the TL sizes are missing (either not evaluable or not read, or the scan was not done) then a scaling up rule will be applied as follows:

- If $\leq 1/3$ of lesions recorded at baseline are missing, then the results will be scaled up (based on the nadir sizes) to give an estimated sum of diameters and this will be used in calculations (This is equivalent to comparing the visit sum of diameters of the non-missing lesions to the nadir sum of diameters excluding the lesions that are missing and determining at what rate the lesions are changing)
- If $> 1/3$ of lesions recorded at baseline are missing, then the TL response will be NE. However, if the sum of non-missing TL diameters would result in PD (i.e., if using a value of 0 for missing lesions, the sum of diameters has still increased by $> 20\%$ or more compared with the smallest sum of diameters on study, and has an absolute increase ≥ 5 mm) PD takes precedence over NE.

A visit response of CR will not be allowed if any of the TL data are missing.

Progression of non-target lesions is outlined below:

Visit Responses	Description

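### Section 8.4.5 derives best objective response in two conflicting ways: the text accepts an unconfirmed CR or PR, the table scores it SD, and the disease control rate changes with the choice

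*Protocol*

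**What the plan says.** Section 2.2 makes BOR the outcome measure of the anti-tumour secondary objective: "Best objective response (OR) to treatment will be assessed by dose level cohort according to Response Evaluation Criteria in Solid Tumours".

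Section 8.4.5 then derives BOR twice.

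- **Text:** "The best objective response (BOR) per subject will be derived as the best response recorded from the start of treatment until disease progression, death". The window also closes when another anti-cancer treatment starts. The data source is given by the words "using the Investigator reported objective response per time point". No confirmation is asked for. Appendix E rates each visit without confirmation and treats confirmatory imaging as a separate, later step.
- **Table:** "The following rules will be used to determine the best objective response in each patient". Its rows give CR or PR only when a response is seen at two assessments, and SD otherwise.

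Between the two, 8.4.5 limits the objective response rate (ORR) to confirmed responses: "Confirmation must occur at least 4 weeks later". Section 8.3.1 defines DCR as the percentage of the full analysis set with a "confirmed best objective response of CR or PR, or a best objective response of SD".

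**The concern.** A patient with one PR that is not seen again has a BOR of PR by the text and SD by the table. The DCR definition makes this more than a labelling matter. Its response limb requires confirmation and its SD limb requires a BOR of SD. Under the text, the unconfirmed PR fits neither limb, so a patient whose target lesions shrank by at least 30% counts as not controlled, while a patient with no change counts as controlled. Under the table the same patient is controlled.

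The cohorts are small (3-6 patients in Table 12, 12 at the MTD/RP2D) and the study is open-label. If the choice between the two rules is left open, it would be made with the responses already visible.

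**Working it through.** The Protocol gives no figure to reproduce here, and no power or alpha calculation applies. The check expands the 8.4.5 table into every visit sequence its rows cover and scores each sequence both ways.

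Rules applied:

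1. *Text BOR* is the best visit response before progression, in the order CR, PR, SD, PD, with UNK never counted as best.
2. *Table BOR* is the entry in the table.
3. *DCR under the text* counts a text BOR of CR or PR where the table also gives CR or PR (that is, the response was seen again), or a text BOR of SD.
4. *DCR under the table* counts a table BOR of CR, PR or SD.

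| Assessments 2; 3; 4 | Sequences | Table BOR | BOR differs | DCR differs |
|---|---|---|---|---|
| PD | 1 | PD | 0 | 0 |
| CR/PR/SD; PD | 3 | SD | 2 | 2 |
| UNK; PD | 1 | PD | 0 | 0 |
| CR/PR/SD; UNK; PD/UNK | 3 x 2 = 6 | SD | 4 | 4 |
| SD/UNK; CR/PR/SD; PD | 2 x 3 = 6 | SD | 4 | 4 |
| UNK; UNK; PD | 1 | PD | 0 | 0 |
| PR; SD; PD | 1 | SD | 1 | 1 |
| PR; CR/PR; PD/UNK | 2 x 2 = 4 | PR | 2 | 0 |
| PR; SD; PR | 1 | PR | 0 | 0 |
| PR; UNK; PR | 1 | PR | 0 | 0 |
| CR; CR; PD | 1 | CR | 0 | 0 |
| CR; UNK; CR | 1 | CR | 0 | 0 |
| **Total** | **27** | | **13** | **11** |

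The 11 sequences (2 + 4 + 4 + 1) are all an unconfirmed CR or PR: CR or PR by the text, SD by the table, outside DCR under the text and inside it under the table. The other 2 are PR, CR, PD and PR, CR, UNK. The text gives CR, the table gives PR, and DCR is the same.

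ORR does not change in any of the 27, because it requires confirmation under either rule (taking the later CR to confirm the earlier PR in the last two).

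Size per patient: 1/6 = 16.7 points for a cohort of 6, and 1/12 = 8.3 points for a cohort of 12. Compared with the table, the text raises the CR/PR share of the BOR distribution by that amount and lowers DCR by the same amount.

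Coverage: no row fits SD, PR, PR, a PR first seen at the second on-study scan and confirmed at the third, and the table stops at Assessment 4. For such patients only the text is left, which is the rule without a confirmation condition.

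Effect of the fix: if the text requires confirmation and scores an unconfirmed response as SD, the 11 sequences become SD under both rules. The 2 PR-then-CR sequences become PR under both if the CR must itself be confirmed to count as CR. The disagreements fall from 13 to 0 for BOR and from 11 to 0 for DCR.

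**The case against.** The strongest reply is that the table governs. It is introduced in mandatory terms for each patient, and a specific rule normally implements the general sentence before it. On that reading an unconfirmed PR is SD, the patient is inside DCR, and the text merely lacks a clause. This is plausible and is probably the intention, but it does not settle the matter. Nothing gives the table precedence, and the text is a complete derivation in itself. Sections 8.3.1 and 8.4.5 both add the word confirmed to BOR when they define ORR, which would be redundant if BOR already required it. The table also does not cover every patient.

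It is also fair to say that DCR is defined only in 8.3.1: it is not listed in Section 2.2, and Section 8.4 does not mention it. That limits the consequence; it does not remove the conflict in BOR, which is listed.

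Four stronger readings might be inferred, and the Protocol does not support them.

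- *That the response rate changes.* It does not, since ORR always requires confirmation.
- *That the table turns every PR followed by an unknown scan into SD.* It does so only if Assessment 4 is PD or UNK; PR, UNK, PR is scored PR.
- *That a confirmed PR starting at the second scan is lost.* No rule scores SD, PR, PR as SD, because the SD-then-PR row applies only when PD follows. The row is simply absent.
- *That the number of affected patients can be projected from the 17 of 176 (9.7%) partial responses in Section 1.2.1.* That figure pools monotherapy with chemotherapy combinations, only nine patients in that study received monotherapy, and no split into confirmed and unconfirmed is given.

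**Conclusion.** Section 8.4.5 is wrong as written. It contains two derivations of a named secondary outcome measure that disagree in 13 of the 27 sequences its own table covers. In 11 of these the DCR of 8.3.1 changes as well, and under the text it does so perversely. The size is 16.7 points of a cohort's BOR split and DCR per affected patient at n=6, or 8.3 points at n=12. The number of affected patients is unknown.

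The counts rest on treating a response as confirmed when the table itself gives CR or PR, and the percentages on 6 or 12 patients in the cohort's full analysis set. ORR and the primary DLT/MTD determination are not touched, and the study plans no formal hypothesis test, so the harm is confined to the descriptive activity tables.

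**What to change.** The change is wording only, with no new data or assessments.

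1. In the text of 8.4.5, state that a BOR of CR or PR requires confirmation at least 4 weeks later, and that an unconfirmed CR or PR is scored SD, as in the table.
2. In 8.3.1, define DCR as the percentage of the full analysis set with a BOR of CR, PR or SD.
3. Keep the table, including PR then CR scored as PR (the CR confirms the PR but is not itself confirmed). Add a row scoring SD, PR, PR as PR, and state that the same rule applies to later assessments up to progression, death or new therapy.
4. Optionally, list unconfirmed responses separately by cohort so that the information is not lost.

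The cost is a few sentences in two sections and one table row.

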8.4.6 Progression-free survival

Progression-free survival (PFS) is defined as the time from date of first dose of AZD1775 until the date of objective disease progression or death (by any cause in the absence of progression) regardless of whether the patient withdraws from therapy or receives another anti-cancer therapy prior to progression.

The PFS will be censored in the following scenarios:

- If the patient has neither PD nor death, the PFS will be censored at last tumour assessment with CR, PR, or SD. Patient cannot be censored at “NE”.
- If patient had PD or Death occurred more than 53 days for the BID or QD 5/2 schedule or 35 days for the 5/9 schedule (2.5 tumour assessment intervals) after previous tumour assessment with CR, PR or SD, the PFS will be censored at the date of previous tumour assessment with CR, PR, or SD.
- If the patient does not have post baseline tumour assessment nor death within 53 days for the BID or QD 5/2 schedule or 35 days for the 5/9 schedule after randomisation/enrolment, the PFS will be censored at Day 1.

PFS (in days) is calculated as:

(Date of death of documented Progression or Censoring) – (Date of randomization) +1

To apply the cut-off date to PFS is to exclude those Tumour assessments after cut-off date and anti-cancer therapy date after cut-off date in the analysis.

Progression-free survival will be derived based on scan/assessment dates not visit dates. If RECIST assessments/scans contributing towards a particular visit are performed on different dates then the date of progression will be determined based on the earliest of the dates of the component that triggered the progression. With regard to censoring, a patient will be censored at the latest of the dates contributing to a particular overall visit assessment.

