- w All patients must receive a 5-HT₃ antagonist, ondansetron (Zofran) 8 mg PO QD or granisetron (Kytril) 1 mg PO QD prior to each dose of AZD1775. If nausea and vomiting continue, a second dose of antiemetics can be taken 8 hours later, if necessary. In addition, dexamethasone 4 mg PO will be given with each AZD1775 dose as a minimum on the first day dosing AZD1775 of every 3-5 days dosing period, unless contraindicated or not well-tolerated. Dexamethasone or the 5-HT₃ antagonist may be given by IV as needed. Please note: aprepitant [Emend] and fosaprepitant are not permitted due to known drug-drug interactions (see Section 6.7.4.2).
- x Due to frequent reports of diarrhoea with AZD1775 administration, vigorous anti-diarrhoeal treatment loperamide (Imodium) is required at the first onset of diarrhoea according to ASCO guidelines. Patients should be instructed to take oral loperamide (Imodium) 2 mg every 2 hours until diarrhoea-free for at least 12 hours.
- y When applicable, tumour markers that are elevated and are used by the Investigator to monitor for tumour response will be collected at baseline, Day 1 of each cycle, at the end of treatment and FPV. The tumour marker analysis will be performed by a local laboratory.
- z Previous individual patient genomic profile reports should be provided for this study.
- aa An optional Pharmacogenetics (PGx) sample will be obtained if the patient consents. If PGx blood sample is not collected at Cycle 1 Day 1, it can be collected any visit until the last study visit. This sample is **optional** and must be taken from patients who have provided informed consent for genetic sampling and analysis.

- bb PK samples will be collected at time of AE possibly related to AZD1775 (unless the last dose of study drug was administered > 1 week prior to the event), when imaging is performed for response assessment and at the end of treatment or progression. PK samples will no longer be required after implementation of CSP Version 5.
- cc Patients discontinuing from AZD1775 in the **absence** of PD should have CT scans performed every 3 months from the last dose of study drug until PD has been assessed by the Investigator or the patient begins a new course of cancer therapy or withdraws from the study. If PD has been assessed, patients will then be followed for survival.

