5.1 Efficacy assessments

5.1.1 Tumour assessments

RECIST v1.1 criteria will be used to assess patient response to treatment. The RECIST v1.1 guidelines for measurable, non-measurable, target lesions (TL) and non-target lesions (NTL) and the objective tumour response criteria (Complete Response [CR], Partial Response [PR], Stable Disease [SD] or progressive disease [PD]) are presented in [Appendix E](#).

The same method of assessment of tumour burden used at baseline (CT scans or magnetic resonance imaging [MRI] of the chest and abdomen/pelvis) must be used at each subsequent follow-up assessment (see [Table 2](#), [Table 3](#), and [Table 4](#)). Tumour imaging studies will be repeated every 8 weeks (± 1 week) relative to date of first dose for patients on the QD 5/9 treatment schema and every 9 weeks (± 1 week) relative to date of first dose for patients on the QD 5/2 treatment schema to assess response until objective disease progression as defined by RECIST v1.1 or withdrawal from study.

Categorisation of objective tumour response assessment will be based on the RECIST v1.1 criteria of response: CR, PR, SD and PD. Target lesion progression will be calculated in comparison to when the tumour burden was at a minimum (i.e. smallest sum of longest diameters previously recorded on study). In the absence of progression, tumour response (CR, PR, or SD) will be calculated in comparison to the baseline tumour measurements obtained before starting treatment.

If the Investigator is in doubt as to whether progression has occurred, particularly with regard to NTLs or the appearance of a new lesion, it is advisable to continue treatment until the next scheduled assessment or sooner if clinically indicated, and reassess the patient's status. If repeat scans confirm progression, then the date of the initial scan should be declared as the date of progression.

To achieve 'unequivocal progression' on the basis of non-target disease, there must be an overall level of substantial worsening in non-target disease such that, even in presence of SD or PR in target disease, the overall tumour burden has increased sufficiently to merit discontinuation of therapy. A modest 'increase' in the size of one or more NTL is usually not sufficient to qualify for unequivocal progression status.

It is important to follow the assessment schedule as closely as possible.

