Baseline assessments should encompass chest, abdomen and pelvis and should additionally investigate areas that may be involved based on signs and symptoms of individual patients and should be performed no more than 28 days before the start of study treatment. Follow-up assessments will be performed every 8-9 weeks (depending on the dosing schedule) +/- 1 week window interval after start of treatment until objective disease progression as defined by RECIST 1.1, or withdrawal from study Any other sites at which new disease is suspected should also be adequately imaged at follow-up.

If an unscheduled assessment was performed and the patient has not progressed, every attempt should be made to perform the subsequent assessments at their scheduled visits. This schedule is to be followed in order to minimise any unintentional bias caused by some patients being assessed at a different frequency than other patients.

Target Lesions (TA)

Documentation of target lesions

A maximum of 5 measurable lesions, with a maximum of 2 lesions per organ (including lymph nodes), representative of all lesions involved should be identified as TL at baseline. Target lesions should be selected on the basis of their size (longest diameter for non-nodal lesions or short axis for nodal lesions), but in addition should be those that lend themselves to reproducible repeated measurements. It may be the case that, on occasion, the largest lesion does not lend itself to reproducible measurement in which circumstance the next largest lesion, which can be measured reproducibly, should be selected.

The site and location of each TL should be documented as well as the longest diameter for non-nodal lesions (or short axis for lymph nodes). All measurements should be recorded in millimeters. At baseline the sum of the diameters for all TL will be calculated and reported as the baseline sum of diameters. At follow-up visits the sum of diameters for all TL will be calculated and reported as the follow-up sum of diameters.

Special cases:

- For TL measurable in 2 or 3 dimensions, always report the longest diameter. For pathological lymph nodes measurable in 2 or 3 dimensions, always report the short axis.
- If the CT/MRI slice thickness used is $> 5\text{mm}$, the minimum size of measurable disease at baseline should be twice the slice thickness of the baseline scan.
- If a lesion has completely disappeared, the longest diameter should be recorded as 0 mm.

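### The PFS censoring limits in Section 8.4.6 are labelled 2.5 scan intervals but equal 2.5 treatment cycles, so they are shorter than one scan interval and censor most on-schedule progressions that follow CR, PR or SD

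*Protocol*

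**What the plan says.** Section 8.4.6 defines PFS as the "time from date of first dose of AZD1775 until the date of objective disease progression or death" and gives three censoring rules.

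- **First bullet:** a patient with neither progression nor death is censored at the last scan showing CR, PR or SD. It has no day limit.
- **Second bullet:** progression or death is censored back to the previous CR, PR or SD scan if it comes "more than 53 days for the BID or QD 5/2 schedule or 35 days for the 5/9 schedule (2.5 tumour assessment intervals") after that scan.
- **Third bullet:** it opens "If the patient does not have post baseline tumour assessment nor death within 53 days" (35 days for 5/9), counts from randomisation or enrolment, and censors at Day 1.

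The formula that follows subtracts "Date of randomization) +1".

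The scan schedule is stated consistently elsewhere. Section 8.4.5 says "assessments are performed every 8 weeks on the BID and QD 5/9 Schedule or 9 weeks on either of the 5/2 Schedules". Section 5.1.1 repeats this for the QD schedules (every 8 weeks "relative to date of first dose for patients on the QD 5/9 treatment schema and every 9 weeks" for 5/2). Appendix E gives "every 8-9 weeks (depending on the dosing schedule) +/- 1 week window interval". Table 2, footnote o, puts the first BID scan at Week 8, in the 7 days before Cycle 5, and then every 4 cycles. Patients who stop treatment without progression have "CT scans performed every 3 months from the last dose of study drug until PD has been assessed by the Investigator" (footnotes to Tables 2 to 4).

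Section 1.5 sets cycles of 14 days for BID and 5/9 and 21 days for 5/2.

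**The concern.** A limit on the gap since the last scan is there to handle patients who missed scans: if two or more were skipped, the progression date is too uncertain to use. A limit of 2.5 scan intervals does that. A limit shorter than one interval does the reverse, because it censors patients who attended on time.

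The events that survive are then weighted towards early deaths and unscheduled scans. Whether a progression counts depends on when the scan happened to fall, and the censoring is tied to the event itself. Kaplan-Meier estimates by cohort would be distorted, and differently for each schedule because the limits differ.

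**Working it through.** **1. Reproducing the printed limits**

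| Schedule | Cycle (days) | Scan interval (days) | 2.5 × cycle | 2.5 × scan interval | Printed limit | Limit ÷ scan interval |
|---|---|---|---|---|---|---|
| QD 5/9 | 14 | 56 | 35 | 140 | 35 | 0.63 |
| QD 5/2 (both) | 21 | 63 | 52.5 | 157.5 | 53 | 0.84 |
| BID | 14 | 56 | 35 | 140 | 53 | 0.95 |

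The QD limits match 2.5 cycles (52.5 rounded up to 53) and do not match 2.5 scan intervals. The BID limit matches neither. All three ratios are below 1.

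**2. Second bullet: progression at the next on-time scan after CR, PR or SD**

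With ±7 days on each scan, the gap between consecutive scans is the interval ±14 days. Assume each scan date is uniform in its window. Counting whole days gives 15 × 15 = 225 equally likely pairs. On a continuous scale the difference of two dates is triangular on ±14, so the chance of a gap at least x days short of nominal is (14 − x)² ÷ 392.

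- **QD 5/9:** the gap is 42–70 days, always over 35. Censored: 100%.
- **QD 5/2:** the gap is 49–77 days. To be within 53 it must be at least 10 days short: 15/225 = 6.7%, or 4²/392 = 4.1%. Censored: about 93–96%.
- **BID:** the gap is 42–70 days. To be within 53 it must be at least 3 days short: 78/225 = 34.7%, or 11²/392 = 30.9%. Censored: about 65–69%.

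Off-treatment scans about 91 days apart exceed every printed limit.

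**3. Third bullet: first scan**

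The first on-time scan falls on Day 49–63 (5/9, limit 35) or Day 56–70 (5/2, limit 53), always after the limit. For BID (limit 53), 5 of 15 days in a ±7 window qualify (33%), or 5 of 8 days if the scan falls in the 7 days before Cycle 5 (63%).

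- *Strict reading* (no scan and no death by the limit): every on-schedule QD patient who does not die early is censored at Day 1, whatever the scan shows.
- *Lenient reading* (no post-baseline scan at all): progression at the first scan has no earlier post-baseline CR, PR or SD scan, so the second bullet does not reach it and it stays an event.

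**4. Overall effect, by simulation**

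The protocol gives no PFS or survival assumption. Assumed here: independent exponential times, median progression 12 weeks, median survival 36 weeks, full follow-up, all scans on schedule.

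| Patients kept as events | QD 5/9 | QD 5/2 | BID |
|---|---|---|---|
| Printed limits, strict reading | about 9% | about 14% | about 31% |
| Printed limits, lenient reading | about 51–56% | about 62–65% | about 71–73% |
| Limits of 140/158 days | 100% | 100% | 100% |

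The spread in the lenient row mainly reflects whether a death after the limit but before the first scan is counted. Four other pairs of medians (progression 8–24 weeks, survival 20–52 weeks) gave about 7–16%, 10–23% and 27–41% on the strict reading, and 41–63%, 54–76% and 66–81% on the lenient one. Other pairs in those ranges move the figures by a few points.

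**5. Check of the corrected limits**

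- On-time gaps are at most 70 or 77 days: kept.
- One missed scan gives at most 2 × 56 + 14 = 126 or 2 × 63 + 14 = 140 days: kept.
- Two missed scans give at least 3 × 56 − 14 = 154 or 3 × 63 − 14 = 175 days: censored.

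This is what a limit of 2.5 intervals should do.

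**The case against.** A reader might infer that PFS becomes inestimable, that only early deaths count, or that no on-schedule QD patient escapes censoring at Day 1. All three need the strict reading of the third bullet. The wording allows the lenient one, and there is an argument for it: on the strict reading the second bullet has almost nothing left to act on for on-schedule QD patients. On the lenient reading, roughly half or more of patients remain events under the 12- and 36-week medians. That part of the objection stands, and the simulated percentages are illustrations under assumptions the protocol does not supply.

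A reader might also infer that almost every scheduled-scan progression is lost on all schedules. That is exact for 5/9 and close for 5/2 for progressions after a CR, PR or SD scan. It is too strong for BID (12 of about 66 planned patients), where the limit is only 3 days short of the interval. Scans done early for clinical reasons can also fall inside the limits.

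Finally, PFS is not a primary, secondary or exploratory outcome in Sections 2.1 to 2.3. The anti-tumour outcome is best objective response, Section 8.4 rules out formal testing, and MTD/RP2D rests on DLTs. This limits the consequence but does not make the numbers right. Nor does the possibility of an SAP help: the protocol fixes explicit values that contradict their own label.

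**Conclusion.** The error is established by arithmetic from the protocol alone: 35 and 53 days are 2.5 cycles, 2.5 scan intervals are 140 and 157.5 days, and BID is placed with the wrong schedule. Every limit is shorter than one scan interval. The share of next-scan progressions censored under the second bullet (all on 5/9, about 93–96% on 5/2, about 65–69% on BID) rests only on uniform ±7-day windows. The overall loss of events depends on the reading of the third bullet and on assumed medians, but PFS is distorted on either reading.

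The time origin is also inconsistent within the section: the definition starts at first dose, while the formula and third bullet use a randomisation date that a non-randomised dose-escalation study does not have.

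The damage is confined to a supportive descriptive PFS summary. The documents do not support extending it to the dose decision or the listed objectives, so this should be corrected before PFS is analysed but is not a critical defect of the trial.

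**What to change.** In Section 8.4.6:

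- In the second and third bullets only, replace the limits with 140 days for BID and QD 5/9 (2.5 × 56) and 158 days for both 5/2 schedules (2.5 × 63 = 157.5, rounded up). The first bullet needs no change.
- Reword the third bullet so that only a patient with no evaluable post-baseline tumour assessment and no death within the limit is censored at Day 1.
- Replace the randomisation and enrolment origins in the formula and third bullet with the date of first dose, to match the section's own definition.

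One off-treatment gap of about 91 days fits within the new limits, so a separate limit for that phase is optional.

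The cost is a few lines of protocol or SAP wording and the matching programming specification. No new data are needed.
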